NON-INTERVENTIONAL (NI) STUDY PROTOCOL

Study Information

Title	Evaluation of the reliability of effect of rimegepant or triptans for the acute treatment of migraine across multiple attacks
Protocol number	C4951066
Protocol version identifier	Final, V2.0 (amendment 1)
Date	23 April 2024
Active substance	Analgesics, calcitonin gene-related peptide (CGRP) antagonists. ATC code: N02CD06
Medicinal product	Rimegepant (Nurtec 75mg ODT)
Research question and objectives	
The objectives of this study are to 1) explore reliability of effect with acute use of rimegepant or triptans; 2) evaluate satisfaction with rimegepant or triptans; 3) evaluate willingness to continue using rimegepant or triptans; 4) explore proportion optimized on treatment with rimegepant or triptans.
 
Research questions:
 
1. What is the reliability of effect of rimegepant or triptans in the real world over multiple migraine attacks when taken PRN?2. How satisfied are patients with rimegepant or triptans to treat their migraine attacks?3. How willing are patients to continue taking rimegepant or triptans to treat their migraine attacks?4. What proportion of those treating acutely with rimegepant or triptans are adequately responding and well managed?5. When do patients administer rimegepant or triptans when treating an acute attack?

Author	PPD	, CPsychol, PPD
	PPD	

This document contains confidential information belonging to Pfizer. Except as otherwise agreed to in writing, by accepting or reviewing this document, you agree to hold this information in confidence and not copy or disclose it to others (except where required by applicable law) or use it for unauthorized purposes. In the event of any actual or suspected breach of this obligation, Pfizer must be promptly notified.

2. LIST OF ABBREVIATIONS

Abbreviation	Definition
AE	Adverse Event
AIDS/HIV	Acquired Immunodeficiency Syndrome/Human Immunodeficiency Virus
ARW	Adelphi Real World
BMI	Body Mass Index
CGRP	Calcitonin Gene-related Peptide
CM	Chronic Migraine
COVID-19	Coronavirus Disease 2019
CV	Cardiovascular
DSP	Disease Specific Programme™
EC	Ethics Committee
ED	Emergency Department
EM	Episodic Migraine
EMA	European Medicines Agency
EphMRA	European Pharmaceutical Market Research Association
GI	Gastrointestinal
IBM	International Business Machines Corporation
IBS	Irritable Bowel Syndrome
ICJME	International Committee of Medical Journal Editors
ICSR	Individual Case Safety Reports
IRB	Institutional Review Board

Abbreviation	Definition
MHD	Monthly Headache Day
MMD	Monthly Migraine Day
m-TOQ6	Migraine Treatment Optimization Questionnaire
NASH	Nonalcoholic Steatohepatitis
NSAIDs	Non-steroidal Anti-inflammatory Drugs
ODT	Orally Disintegrating Tablet
PCP	Primary Care Physician
PRF	Patient Record Form
PRN	Pro Re Nata
PRO	Patient-reported Outcome
PSC	Patient Self Completion
QoL	Quality of Life
RWD	Real World Data
Rx	Prescription
SAP	Statistical Analysis Plan
SD	Standard Deviation
SPSS	Statistical Package for the Social Sciences
SUNCT	Short-lasting, Unilateral, Neuralgiform headache attacks with Conjunctival injection and Tearing
TIA	Transient Ischemic Attack
US	United States of America
YLD	Years Lived with Disability

4. ABSTRACT

Stand alone document.

AMENDMENTS AND UPDATES

Amendment 1

This amendment is to add a descriptive analysis of triptans compared to rimegepant for the acute treatment of migraine attacks.

Version Identifier	Date	Amendment Type (substantial or administrative)	Protocol Section(s) Changed	Summary of Amendment(s)	Reason
Version 2.0	23 April 2024	Administrative	3. Responsible parties	PIs updated	Clinical scientist joined the team, and changes to vendor team
Version 2.0	23 April 2024	Administrative	6. Milestones	Timelines for additional analyses & reporting added	Provide data for China NRDL submission
Version 2.0	23 April 2024	Substantial	8 – Research Objectives 9.2 Setting 9.2.1 Inclusion criteria 9.2.2 Exclusion criteria 9.3 Variables 9.6 Data analysis 9.6.1 Analysis Plan 9.6.2 Analysis Plan for Objective 1 9.6.3 Analysis Plan for Objective 2 9.6.4 Analysis Plan for Objective 3 9.6.5 Analysis Plan for Objective 4	Addition of triptans as treatment of interest. For descriptive analysis only.	Provide data for China NRDL submission
Version 2.0	23 April 2024	Substantial	9.5 Study size	Sample size updated to include triptan population.	Provide data for China NRDL submission

5. MILESTONES

Milestone	Planned Date
Protocol/SAP (Version 1.0)	7 Dec 2023
Data collection started (Version 1.0)	2 Jan 2024
Data collection completed (Version 1.0)	3 Jan 2024
Final study tables (Version 1.0)	29 Jan 2024
Protocol/SAP (amendment V.1.)	23 Apr 2024
Final study tables (Phase V1.1)	30 April 2024
Final report	02 Dec 2024
Abstract 1	17 Feb 2024
Abstract 2	17 May 2024

6. RATIONALE AND BACKGROUND

Migraine is a common, often disabling neurologic disease characterized by recurrent attacks of head pain that are typically unilateral, throbbing, and associated with a range of symptoms that may include photophobia, phonophobia, nausea, and vomiting.¹⁻³ Migraine can be classified as episodic or chronic based on the frequency of the migraine or headache: episodic migraine (EM) is characterized by one to 14 monthly headache days (MHDs) or monthly migraine days (MMDs), while chronic migraine (CM) is characterized by 15 or more MHDs for at least three months, with at least eight days a month on which the headaches and associated symptoms meet diagnostic criteria for migraine.^{1,3,4} Migraine is a clinically complex disorder, and in addition to its direct clinical burden, patients experience a greater number of comorbidities compared to those without migraine.⁵

In 2019, an estimated 1.1 billion people in the world suffered from migraine, causing 42.1 million years lived with disability (YLD).⁶ Women are two to three times more likely than men to be affected by migraine.⁷⁻⁹ The global age-standardized prevalence of migraine was 14.1% in 2019, which is an increase of 1.7% since 1990. There were 87.6 million incident cases of migraine globally in 2019, resulting in an incidence of 11.4%, which was an increase of 2.1% since 1990.⁶

In the US, migraine accounted for \$36 billion in both direct and indirect costs in 2016.¹⁰ The three most common locations for migraine care are primary care, neurologist, and emergency department (ED) settings, with approximately 1.2 million ED visits in the US annually due to migraine attacks.¹¹ Indirect costs related to work productivity impairment are commonly incurred in patients with migraine, with presenteeism accounting for the majority of work-related productivity loss.^{12,13} Annual costs due to migraine-related lost productivity in the US were estimated at \$2.1 million for the manufacturing sector and \$2.9 million for the service sector (per 10,000 individuals).¹⁴ Patients with refractory migraine have higher mean annual frequency of outpatient visits, ED visits and admissions, and a higher intensity of care vs. patients with migraine and those without migraine.¹⁵

While treatment goals vary by region, guidelines from both the US and France (the most recently published treatment goals in Europe) for acute migraine treatment suggest these are rapid and sustained freedom from pain, improvement in other migraine symptoms, and minimal or no adverse events (AEs).^{16,17} There is significant need for effective and tolerable treatments for migraine sufferers, especially those who experience at least four migraine days per month. In these patients, preventive treatment is recommended to reduce migraine-related disability and the overuse of acute therapies and rescue medication.¹⁶ Both US and European guidelines note the importance of reduced attack frequency, reduction or maintenance (no escalation) of acute treatment use, and an improvement in quality of life (QoL).^{16,17} Current migraine treatments leave millions of people who have migraine with unmet needs due to lack of and/or insufficient efficacy, AEs, and contraindications.^{18,19}

Rimegepant (VYDURA®/NURTEC® ODT), a next-generation, small molecule oral selective and potent calcitonin gene-related peptide (CGRP) receptor antagonist, is the first and only migraine treatment approved for both the acute treatment of migraine with or without aura in adults and for the preventive treatment of EM in adults who have at least four migraine attacks per month. Prior to rimegepant, there was no single medication proven to be safe and effective for both acute and preventive treatment of migraine. Rimegepant was approved in the US for the acute treatment of migraine in February 2020, and for preventive treatment of episodic migraine in adults who have at least 4 migraine attacks per month in May 2021. It was approved by the EMA for both indications in April 2022.

The Adelphi Real World (ARW) Migraine Disease Specific Programme™ (DSP) 2022 surveys provide an opportunity to examine physician and patient perspectives for rimegepant in the US. This protocol describes the analysis of ARW Migraine VII DSP™ as a secondary real-world data (RWD) source to address the research questions.

7. RESEARCH QUESTION AND OBJECTIVES

The objectives of this study are to 1) explore reliability of effect with acute use of rimegepant or triptans; 2) evaluate satisfaction with rimegepant or triptans; 3) evaluate willingness to continue using rimegepant or triptans; 4) explore proportion optimized on treatment with rimegepant or triptans.

Research questions:

1. What is the reliability of effect of rimegepant or triptans in the real world over multiple migraine attacks when taken PRN?
2. How satisfied are patients with rimegepant or triptans to treat their migraine attacks?
3. How willing are patients to continue taking rimegepant or triptans to treat their migraine attacks?
4. What proportion of those treating acutely with rimegepant or triptans are adequately responding and well managed?
5. When do patients administer rimegepant or triptans when treating an acute attack?

8. RESEARCH METHODS

8.1. Study Design

A cross-sectional study design using physician and patient survey data drawn from the ARW Migraine VII DSP will be employed to assess the acute use of, satisfaction with, willingness to continue use and treatment optimization of rimegepant or triptans in patients with migraine. Participants were recruited into the Migraine VII DSP in the US between May 2022 and November 2022. This study comprises a secondary data analysis of DSP data.

The full DSP methodology has been published and validated and the illustration below outlines the main phases of the DSP].^{20,21,22} The DSP was conducted across a number of countries including the EU5 and US. Given the timing of the data collection, only data from the US will be utilized as rimegepant was available on the US market at the time of administration, unlike for other countries.

The ARW DSP™ are made available to subscribers upon the strict condition that all information remains the intellectual property of ARW and should not be divulged to any third party except with the written prior permission of ARW. Pfizer has subscribed to access the ARW Migraine VII DSP and so cannot be considered as the Study Sponsor.

8.2. Setting

ARW works with field partners across the US with the same principle of physician-based recruitment for all DSPs. Both physician-level and patient-level data are available for analyses of the migraine DSP (see [Figure 1](#)).

The study population will comprise of consulting patients included in the Migraine VII DSP between May 2022 and November 2022; namely, consulting adult patients diagnosed with migraine and prescribed rimegepant or triptans as an acute treatment for their migraine in the US.

DSP physician participants for the migraine DSP in the US were neurologists and general physicians identified from public lists of healthcare professionals and meeting the following criteria:

- Physicians identified as a PCP or neurologist.
- PCPs must make treatment decisions for at least 10 patients with migraine and neurologists must make treatment decisions for at least 20 patients with migraine.

Candidate respondents were screened online and those who met the predefined eligibility criteria were invited to participate (see [Section 8.2.1](#) and [Section 8.2.2](#)).

[figure not shown]
Each participating physician was asked to provide patient data for up 8 patients with migraine. Patient data for the migraine DSP was based on patients aged 18 years or older with a diagnosis of migraine and not involved in a clinical trial.

As described in Figure 1, during the US survey period (May–November 2022), physicians involved in the management of migraine patients were recruited to complete an online survey (Physician Survey) of their attitudes and behaviors regarding the treatment of migraine. Each physician then completed an electronic Patient Record Forms (PRFs) on 8 consecutive consulting patients with migraine, regardless of the reason for the visit. The consecutive approach to recruitment was stressed to each participating physician to remove the element of selection bias. A generic copy of the data collection forms for Physicians is included in APPENDIX 2. COPIES OF PATIENT RECORD FORM (PRF), PATIENT SELF COMPLETION (PSC) QUESTIONNAIRES and PHYSICIAN SURVEY QUESTIONNAIRES: ENGLISH LANGUAGE VERSION.

The patients were then asked if they would be willing to complete a pen-and-paper Patient Self-Completion (PSC) questionnaire about their experiences of having migraine. This allows a unique view of the disease from both the patient and physician perspective. Completion of the PSC by the patient was voluntary.

Figure 1. Migraine DSP Data Collection Methodology

Migraine VII (22/23) – DSP™ Methodology

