8.5. Study Size

Given the primary research objective is purely descriptive in nature (i.e., no *a priori* hypotheses specified), the available sample size is fixed by the DSP data collection methodology and simply impacts the precision of any estimates. Therefore, formal sample size calculations are not applicable and have not been performed. All patients who meet the eligibility criteria will be included in the study. For this study, the sample size is 528 (91 Rimegepant, 437 Triptans) for the physician-reported outcomes, and 143 (29 Rimegepant, 113 Triptans) for the patient-reported outcomes. Data Management

Pseudoanonymised data are taken from the Migraine VII DSP, which is owned and managed by ARW.

All data analysis will be conducted using Stata 17 software, version 17.0 (StataCorp, College Station, Texas) / IBM® SPSS® Data Collection Survey Reporter v7.5 or the latest available version at time of analysis. All programming code/ syntax written to conduct the required analysis will be logged for transparency and replicability.

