8.6. Data Analysis

Analyses will be based on patients receiving rimegepant or triptans only as an acute treatment currently for their migraine.

Data will be stratified by time spent on rimegepant or triptans and number of migraine related headache days.

Analysis will be descriptive. The mean, standard deviation (SD), median, 25th and 75th percentiles and minimum and maximum values will be reported for numeric variables, whilst relative frequencies and percentages will be reported for categorical variables.

The real-world nature of the DSP means many variables will contain missing data. We would expect the base of patients to vary from variable to variable due to imperfect physician knowledge, physicians not wishing to answer the question, etc. The base relevant to each analysis will be reported in any data tables provided. There will be no imputation of missing data. Where missing values are found in a particular variable, any patients with missing values will be removed from all pieces of analysis where that variable is used. However, patients removed from one piece of analysis are still eligible for inclusion in other analyses. In the derivation of PRO variables, the handling of missing data will follow the official instructions as provided by the author/owner of the PRO questionnaire.

Detailed methodology for summary and statistical analyses of data collected in this study is documented in a statistical analysis plan (SAP) below:

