Patient current preventive treatment(s)	PRF EQ1	Proportion of responses to: Yes / No, but this patient has received preventive prescribed treatment(s) for their migraine in the past / No, and this patient has never received prescribed preventive treatment(s) for their migraine
Patient receiving preventive treatment(s) previously	PRF EQ3 PRF EQ10	Proportion of responses to: Anti-CGRP mAbs, Anticonvulsants, Beta-blockers, Anti-CGRP gepant, Antidepressant/Anxiolytics/Benzodiazepines / Calcium antagonists / Contraceptive / NSAIDs (including combinations), Opioid analgesics (including combinations) Neurotoxins / Other / No drug treatment Responses of ‘No treatment’ will be omitted from analysis. Responses of ‘Rimegepant’ will be omitted from analysis. Proportion of responses to: Anti-CGRP mAbs, Anticonvulsants, Beta-blockers, Anti-CGRP gepant, Antidepressant/Anxiolytics/Benzodiazepines / Calcium antagonists / Contraceptive / NSAIDs (including combinations), Opioid analgesics (including combinations) Neurotoxins / Other / No drug treatment Responses of ‘No treatment’ will be omitted from analysis.

8.6.2. Analysis Plan for Objective 1

Objective 1 focuses on the reliability of effect of rimegepant or triptans over multiple attacks when taken PRN to treat migraine. This will be addressed by describing the following:

Variable	Data Source(s)	Analysis Plan
Failure to achieve pain freedom within 2 hours post dose (physician perspective)	PRF DQ18	Proportion of responses to: Yes / No Responses of “Don’t know” will be omitted from analysis.

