
PFIZER CONFIDENTIAL

CT24-WI-GL02-RF02 5.0 Non-Interventional Study Protocol Template For Secondary Data Collection Study

01-Aug-2023

Page 27 of 36

Variable	Data Source(s)	Analysis Plan
		drug / On local/national formulary / Clinical trial/publication evidence / Other selected for rimegepant or triptans
Number of migraine attacks acute treatment achieves pain freedom within 2 hours post dose (patient perspective)	PSC HQ6	
Proportion of responses to: 0 out of every 5 attacks / 1 out of every 5 attacks / 2 out of every 5 attacks / 3 out of every 5 attacks / 4 out of every 5 attacks / 5 out of every 5 attacks
 
Success will be defined as responses to '4 out of every 5 attacks' or '5 out of every 5 attacks' combined

8.6.3. Analysis for Objective 2

Objective 2 focuses on satisfaction of physicians and patients with rimegepant or triptans to treat migraine acutely. This will be addressed by describing the following:

Variable	Data Source(s)	Analysis Plan
Satisfaction with current acute treatment (physician perspective)	PRF IQ1a	
Proportion of responses to: Extremely satisfied / Satisfied / Slightly Satisfied / Neither satisfied nor dissatisfied / Slightly dissatisfied / Dissatisfied / Extremely dissatisfied
 
Satisfaction will be defined as responses to: 'Extremely satisfied' or 'Satisfied' or 'Slightly Satisfied' combined
 
Dissatisfaction will be defined as responses to: 'Neither satisfied nor dissatisfied' or 'Slightly dissatisfied' or 'Dissatisfied' or 'Extremely dissatisfied' combined
 
Data to be matched to PSC equivalent data (PSC HQ18a)

Drivers for lack of satisfaction with current acute treatment (physician perspective)	PRF IQ1b	Proportion of responses to: Lack of efficacy / Slow onset of action / Efficacy diminished over time / Number of side effects experienced / Severity of side effects experienced / Mode of administration / Complicated dosing regimen / The number of prescribed acute treatments / The treatment is costly for the patient / Other

Variable	Data Source(s)	Analysis Plan

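### Physician-reported outcomes for rimegepant and triptans are pooled over PCPs and neurologists, and no planned table shows whether the specialty mix differs between the two drug groups

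*Combined protocol and SAP*

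**What the plan says.** Section 8.2 recruits by specialty ("Physicians identified as a PCP or neurologist") and sets a different caseload threshold for each: "PCPs must make treatment decisions for at least 10 patients with migraine and neurologists must make treatment decisions for at least 20 patients with migraine". It also states the per-physician cap: "Each participating physician was asked to provide patient data for up 8 patients with migraine". The same section says that physician-level as well as patient-level data are available for analysis.

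Four items from the physician's record form serve as outcomes. Section 8.6.2 has DQ18 ("Failure to achieve pain freedom within 2 hours post dose (physician perspective") and FQ1a, the reason for choosing the drug. Section 8.6.3 has IQ1a ("Satisfaction with current acute treatment (physician perspective") and IQ1b, the drivers of any lack of satisfaction. Each is summarised as proportions of responses.

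Section 8.5 gives the numbers: "For this study, the sample size is 528 (91 Rimegepant, 437 Triptans) for the physician-reported outcomes". Section 8.6 says "Analysis will be descriptive" and names two strata: "Data will be stratified by time spent on rimegepant or triptans and number of migraine related headache days". Physician specialty, the number of contributing physicians and the number of patients per physician are absent from Table 1 and from Sections 8.6.1 to 8.6.5.

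The Amendments and Updates section says that Amendment 1 adds triptans for a descriptive comparison with rimegepant, to supply data for a China NRDL submission.

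**The concern.** The treating physician supplies all four items. PCPs and neurologists may see different patients, apply different standards when recording failure or satisfaction, and prescribe the two drugs in different proportions. If so, pooled percentages set side by side partly compare who did the rating and in what setting.

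Specialty belongs to the rater, so describing patient age, severity or comorbidity does not display it. The two planned strata do not either. The bases that Section 8.6 promises count patients, not physicians. The limitations in Section 8.8 cover selection, recall and unverified self-report, but not differences between raters or specialties.

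At stake is how the rimegepant and triptan columns are read. With no test or model planned, the tables are the reader's only protection.

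**Working it through.** **1. Stated sample size.** Section 8.5: 91 + 437 = 528, which agrees with the stated total. There is no power calculation to reproduce.

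**2. Where specialty appears.**
- Section 8.2: entry criterion, so it should be held for every physician (an inference, but a strong one).
- Table 1 and Section 8.6.1: not listed.
- Section 8.6 strata: time on drug and headache days only.
- Sections 8.6.2 and 8.6.3: pooled proportions.

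**3. Effect of specialty mix.** Let *s* be the neurologist share in a drug group, *a* the rate recorded by neurologists and *b* the rate recorded by PCPs, the same for both drugs.

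Pooled rate = *s·a* + (1 − *s*)*·b*

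Gap with no drug difference = (*s*_rimegepant − *s*_triptan) × (*a* − *b*)

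None of these inputs is in the documents. The values below are assumed, and the direction could be either way.
- With *a* = 55%, *b* = 40% and neurologist shares of 80% and 40%: rimegepant 0.8 × 55 + 0.2 × 40 = 52%; triptans 0.4 × 55 + 0.6 × 40 = 46%; gap 6 points.
- With the same 15-point rating gap: a mix difference of 10 points gives 0.10 × 15 = 1.5 points, and 60 points gives 0.60 × 15 = 9 points.
- With a rating gap of 5 to 30 points and a mix difference of 10 to 40 points: 0.10 × 5 = 0.5 points up to 0.40 × 30 = 12 points.
- If either difference is zero, the gap is zero.

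For scale, the 95% half-width of the pooled difference at p = 0.5, with records taken as independent, is 1.96 × √(0.25/91 + 0.25/437) = 11.3 points. Most of the assumed range lies inside sampling error, but it is a shift that a larger sample would not remove.

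**4. Number of raters (bounds only).**
- At the cap of 8: 91/8 = 11.4, so at least 12 physicians for rimegepant; 437/8 = 54.6, so at least 55 for triptans. One physician with 8 records would carry 8/91 = 8.8% or 8/437 = 1.8% of the estimate.
- At one record per physician: 1/91 = 1.1% or 1/437 = 0.2%.

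The cap covers all consecutive migraine patients, whatever their treatment, so the number per physician within one drug group is probably well below 8.

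**5. Clustering, kept separate.** Several records per physician mainly affect precision. The design effect is 1 + (*m* − 1) × ICC. With assumed *m* of 2 to 8 and ICC of 0.05 to 0.30 it runs from 1.05 to 3.1, which takes the effective rimegepant sample from 91 to between 87 and 29. The plan reports no intervals, so no stated figure is affected.

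**6. Cost of splitting.** With 80% of rimegepant records from neurologists, PCP records number 0.2 × 91 ≈ 18. At p = 0.5 the 95% half-width is 1.96 × √(0.25/18) = 23 points for PCPs and 1.96 × √(0.25/73) = 11.5 points for neurologists.

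**The case against.** The strongest reply is that the plan draws no inference. It has no hypotheses, tests, intervals or between-drug estimate, its research questions ask about each treatment rather than a difference, and Section 8.8 disclaims causal conclusions. That lowers the severity but does not answer the point. Amendment 1 exists to put the two columns next to each other, and Section 8.8 says that associations can be identified.

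Second, patient-reported measures exist. IQ1a is to be matched to the patient's own rating (HQ18a), 2-hour pain freedom has a patient version (HQ6), and Objectives 3 and 4 rest on patient reports. This stands as a limit on scope: only parts of Objectives 1 and 2 are affected. The matching compares physician with patient, and does not show whether one drug group was rated by a different mix of specialties.

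Third, the items differ in kind. DQ18 is a report of failure, and physicians could consult records. FQ1a asks for the prescriber's reasons, so a specialty difference there is part of the answer. Both remarks are fair. It would be wrong to call all four items mere opinion, but all four still depend on who completed the form.

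Fourth, within-specialty cells may be too small to carry conclusions. This stands, and it limits the fix.

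A reader might also infer that some 12 physicians supplied the rimegepant data, or that clustering by itself biases the contrast. The documents support neither: 12 is a lower bound at the cap, and clustering mainly concerns precision, although a few heavy contributors could move the smaller group.

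**Conclusion.** The point holds as a gap in description. Four physician-reported items are shown for two drugs, pooled over two specialties, and nothing planned would tell a reader whether the specialty mix is the same in both groups. A distortion requires both an unequal mix and a rating difference between specialties. The documents give neither, so its size and direction are unknown. The illustrative 1.5 to 9 points rests on an assumed 15-point rating gap and a mix difference of 10 to 60 points.

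A reader might go further and conclude that any physician-reported difference between the drugs is a rater artefact. The documents do not support that, since the mixes may turn out similar. Nor would a split by specialty separate rating habit from the kind of patient seen in each setting; it would only show whether the difference persists within specialty. The change is worth making because it is cheap and the comparison is the purpose of the amendment.

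**What to change.** **Section 8.6.1.** For each drug group, add physician specialty (PCP or neurologist), the number of contributing physicians and the maximum number of patients from one physician.

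**Sections 8.6.2 and 8.6.3.** Show DQ18 and IQ1a (satisfied versus dissatisfied, as already defined) by specialty within each drug group, beside the pooled figures and with the base of every cell. For FQ1a, split only the consistency-of-response option; the full list has too many options for cells of this size.

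**Reporting rule.** Where the specialty mix differs between the drug groups and the within-specialty figures do not show the same direction as the pooled ones, describe the pooled difference as possibly reflecting specialty mix. Do not require every statement to rest on within-specialty cells. Add a sentence on this to Section 8.8.

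**Cost.** SAP wording and a few table rows and columns, with no new data, since specialty was an entry criterion. The drawback is small rimegepant cells, so the split supports the pooled table and does not replace it. The milestones put the additional tables at 30 April 2024 and the final report at 2 December 2024, which leaves room for supplementary tables.
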